1. SYNOPSIS

AEGERION PHARMACEUTICA	ALS, INC.
MYALEPT	
Metreleptin	
Protocol AEGR-734-401	
A 36-Month, Multicenter, Op Evaluate the Immunogenicity Treatment in Patients with Go	of Daily SC Metreleptin
The study will be conducted at approximately 10 study centers in the United States (US).	
Phase 4	
Primary Objective: Evaluate the immunogenicity associated with daily SC metreleptin treatment in patients with congenital or acquired generalized lipodystrophy. Secondary Objective: Assess 2 methods of measuring in vitro neutralizing activity to metreleptin.	Outcome Measure: Anti-metreleptin, anti human leptin (anti-HuL) binding antibody titers over time. Category of in vitro neutralizing activity to metreleptin in a cell-based assay and titer in a receptor-binding assay in metreleptin/leptin- antibody positive samples over time. Outcome Measure: Receptor-binding assay titer, cell-based assay category.
	MYALEPT Metreleptin Protocol AEGR-734-401 A 36-Month, Multicenter, Operaluate the Immunogenicity Treatment in Patients with Grant The study will be conducted in the United States (US). Phase 4 Primary Objective: Evaluate the immunogenicity associated with daily SC metreleptin treatment in patients with congenital or acquired generalized lipodystrophy. Secondary Objective: Assess 2 methods of measuring in vitro neutralizing activity to

Confidential Page 10 of 60

	Safety Objectives:	Outcome Measure:	
	Evaluate the safety and tolerability in relation to the development of or absence of anti-metreleptin or anti-huL antibodies, and/or in vitro neutralizing activity to metreleptin in patients with congenital or acquired generalized lipodystrophy.	SAEs, adverse events leading to discontinuation, loss of response (as assessed by HbA1c and serum triglycerides), severe infections and/or sepsis, standard laboratory tests, and vital signs over time.	
	Measure in vitro neutralizing activity in all patients with suspected loss of response (worsening of metabolic control) or endogenous leptin action (severe infections or sepsis) at time of adverse event report.	Receptor-binding assay titer, cell-based assay category.	
	Exploratory Objective:	Outcome Measure:	
	Evaluate the efficacy achieved with daily SC metreleptin treatment in patients with congenital or acquired generalized lipodystrophy.	Change from baseline in HbA1c and fasting triglycerides over time.	

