3.3 Safety Objectives

Safety Objectives: Outcome Measure:

Evaluate the safety and tolerability in relation to the development of or absence of anti-metreleptin or anti-huL antibodies, and/or *in vitro* neutralizing activity to metreleptin in patients with congenital or acquired generalized lipodystrophy.

Measure in vitro neutralizing activity in all

Measure *in vitro* neutralizing activity in all patients with suspected loss of response (worsening of metabolic control) or endogenous leptin action (severe infections or sepsis) at time of adverse event report.

SAEs, adverse events leading to discontinuation, loss of response (as assessed by HbA1c and serum triglycerides), severe infections and/or sepsis, standard laboratory tests, and vital signs over time.

Receptor-binding assay titer, cell-based assay category.

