10.5 Methods for Statistical Analyses

There will be no hypothesis testing. All data will be summarized by descriptive statistics and/or listings. In general, continuous variables will be summarized by n, mean, SD, median, min and max. Number of patients and percentage of patients in a category will be provided.

Descriptive statistics will be provided for immunogenicity variables (Section 10.4). The maximum antibody titer (anti-metreleptin or anti-HuL) during a visit will be summarized by visit. Categorization of *in vitro* neutralizing activity as assessed by cell-based assay will be summarized across visits; the rate of Category D and E *in vitro* neutralizing activity with 90% and 80% exact confidence intervals will be computed. The results are reported as percent inhibition and 80% inhibition is currently utilized as the neutralizing antibody threshold. activity Results for *in vitro* neutralizing activity will be summarized across visits; however, there will be no formal comparison of the 2 assay methods for the detection and relative potency of Category D or E *in vitro* neutralizing activity.

Maximum antibody titers, neutralizing activities detected by both methods, and metreleptin exposure for each patient will be plotted over time. Maximum antibody

Confidential Page 47 of 58

titers, neutralizing activities detected by both methods, and any associated clinical events (i.e., loss of efficacy or AE) will be summarized.

All AEs will be coded using the Medical Dictionary for Regulatory Activities (MedDRA). The number and percentage of patients who experienced at least 1 AE will be summarized by system organ class and preferred term. AEs will be summarized by relationship to the study medication and by severity. Deaths, SAEs, AESIs, and AEs leading to discontinuation will be tabulated and/or listed. SAEs, AESIs and AEs leading to discontinuation will be summarized respectively by peak antibody titers (antimetreleptin, anti-HuL) and by *in vitro* neutralizing activity categories or percent inhibition.

Clinical laboratory results (hematology, chemistry, and urinalysis), and vital signs results will be summarized using descriptive statistics for each visit.

Change from baseline in HbA1c and percent change from baseline in fasting triglycerides will be summarized for each visit by overall patient population, by peak antibody titers (anti-metreleptin, anti HuL), and by *in vitro* neutralizing activity categories or percent inhibition , respectively.

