#### 3.3 Safety Objectives

The safety objectives are:

- To evaluate the safety and tolerability in relation to the development of or absence of antimetreleptin or anti-human leptin (HuL) antibodies, and/or *in vitro* neutralizing activity to metreleptin in patients with congenital or acquired generalized lipodystrophy.
- To measure *in vitro* neutralizing activity in all patients with suspected loss of response (worsening of metabolic control) or endogenous leptin action (severe infections or sepsis) at time of adverse event report.

Document: Statistical Analysis Plan: AEGR-734-401: A 36-Month, Multicenter, Open Label Phase 4 Study to Evaluate the

Immunogenicity of Daily SC Metreleptin Treatment in Patients with Generalized Lipodystrophy

Author: [name], [name], [name], [name] Version Number: 2.1

Page 11 of 25

Statistical Analysis Plan

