### 18. EXPLORATORY ANALYSES – EFFECTIVENESS

The exploratory analyses will be performed using the EAS population.

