#### 18.2 Exploratory Analysis Description, Derivations, and Definitions

Exploratory variables will be summarized using descriptive statistics (see **Section 8.1** Statistical Summaries, Tests and Confidence Intervals) and results will be presented as described below below:

- by visit
- as absolute change from baseline and percent change from baseline at each visit

HbA1c, fasting plasma glucose, and triglycerides will also be summarized by clinically relevant categories at each visit:

- $\circ$  hbA1c (<8%, >=8%)
- o fasting plasma glucose (<70 mg/dL, >=70 mg/dL and <=100 mg/dL, <100 mg/dL)

Document:	Statistical Analysis Plan: AEGR-734-401: A 36-Month, Multicenter, C	Open Label Phase 4 Study to Ev	aluate the
	Immunogenicity of Daily SC Metreleptin Treatment in Patients with	Generalized Lipodystrophy	
Author:	[name], [name], [name], [name]	Version Number:	2.1
		Version Date:	131// 1202/

o triglycerides (<500 mg/dl, >=500 mg/dl).

See Section 8.1 Statistical Summaries, Tests and Confidence Intervals for a description of statistics to be reported.

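### Loss of response is a named safety outcome, but the available SAP text neither derives it nor keeps the protocol's split of HbA1c and triglyceride change by antibody status

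*SAP*

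**What the plan says.** **The outcome.** The Protocol synopsis lists among the safety outcome measures "loss of response (as assessed by HbA1c and serum triglycerides), severe infections and/or sepsis, standard laboratory tests, and vital signs over time"; Protocol 3.3 repeats this. Neither gives an amount of worsening, a reference value or a confirmation rule.

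**The promised analysis.** Protocol 10.5 states that titers, both neutralizing results and "any associated clinical events (i.e., loss of efficacy or AE) will be summarized". It also promises change in HbA1c and percent change in fasting triglycerides at each visit, overall, by peak antibody titer, and by neutralizing category or percent inhibition.

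**The SAP.** SAP 18.2 gives three presentations: values by visit; "as absolute change from baseline and percent change from baseline at each visit"; and "HbA1c, fasting plasma glucose, and triglycerides will also be summarized by clinically relevant categories at each visit", with cuts at 8% for HbA1c and 500 mg/dL for triglycerides. On the analysis set, SAP 18 says "The exploratory analyses will be performed using the EAS population". No presentation is split by antibody status. SAP 17, the safety section, contains adverse events, examinations, vital signs and laboratory summaries, but no loss-of-response variable. SAP 2 says the SAP overrides the protocol where methods differ, and SAP 4.3 says there are no differences.

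**Adverse events of special interest (AESIs).** Protocol 8.3.8 treats suspected loss of response as an AESI. The AESI lists in Protocol 8.2 and SAP 17.1 leave it out.

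**The concern.** Loss of drug effect through neutralizing antibodies is one of the two possible consequences named in Protocol 2.1; the other is inhibition of endogenous leptin. Protocol 2.1 describes the postmarketing requirement as including neutralizing-activity testing in patients with loss of effect and an analysis over time of clinical events associated with antibodies.

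Loss of response is a within-patient sequence: improvement on treatment, then worsening. A group summary against the pre-treatment value does not measure that sequence. Without the antibody split, nothing in SAP 18.2 connects metabolic course to antibody status either. If the SAP is followed as it stands, the link the trial was set up to describe has no prespecified metabolic analysis, although HbA1c and lipids are scheduled at all 10 post-dose visits (Protocol Table 1).

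**Working it through.** The plan states no figure for this outcome and tests no hypothesis (SAP 8.1), so there is nothing to reproduce. The check sets protocol against SAP, then tries the SAP summaries on assumed patients.

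**1. Promise against plan**

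| Protocol | Available SAP text |
|---|---|
| 3.3: loss of response is a safety outcome | 17: no such variable |
| 10.5: loss of efficacy summarized with titers and neutralizing activity | No equivalent; 17.1 covers only what is reported as an adverse event |
| 10.5: HbA1c and triglyceride change by peak titer and neutralizing result | 18.2: whole group only |

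**2. Assumed patients** (baseline, best on treatment, later). The documents give no patient values. Change is later − reference for HbA1c, and later/reference − 1 for triglycerides.

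| Course | From baseline | From best | Category, best to later |
|---|---|---|---|
| HbA1c 9.5, 5.8, 7.8% | 7.8 − 9.5 = −1.7 | 7.8 − 5.8 = +2.0 | below 8%, unchanged |
| HbA1c 12.0, 8.2, 11.0% | 11.0 − 12.0 = −1.0 | 11.0 − 8.2 = +2.8 | 8% or more, unchanged |
| Triglycerides 1,500, 200, 480 mg/dL | 480/1,500 − 1 = −68% | 480/200 − 1 = +140% | below 500, unchanged |
| HbA1c 10.0, 6.5, 9.0% | 9.0 − 10.0 = −1.0 | 9.0 − 6.5 = +2.5 | crosses 8% |
| Triglycerides 1,500, 300, 900 mg/dL | 900/1,500 − 1 = −40% | 900/300 − 1 = +200% | crosses 500 |
| HbA1c 10.0, 6.5, 10.3% | 10.3 − 10.0 = +0.3 | 10.3 − 6.5 = +3.8 | crosses 8% |

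The first three courses still read as improved and do not change category on treatment. The fourth and fifth are registered by the categories. The last is registered by both measures.

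**3. Group summaries by visit.** Assume 10 patients, all with baseline HbA1c 10.0% and all at 7.0%: mean change −3.0. One then rises to 9.5%: (9 × −3.0 + (−0.5))/10 = −2.75. The count at 8% or more rises by one and the maximum moves to −0.5, but a by-visit table cannot tell a patient who relapsed from one who never responded.

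**4. How noisy is a rise from best?** Assume 10 post-dose values with independent normal noise and no true change. The expected rise at the tenth value above the lowest of the first nine is minus the expected minimum of nine standard normals, 1.49, so about 1.5 within-patient SD. A yes/no flag for any rise above the earlier minimum at two consecutive visits would, by simulation, mark 99.7% of such patients. The measure is usable as a continuous display but not as that flag.

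**The case against.** The strongest reply is that SAP 18.2 does more than change from baseline. It also gives values by visit and categories that do not depend on baseline, and these catch some relapses. That stands. A reader might infer that the SAP looks only at change from baseline, or that any patient who loses response will count as improved. The documents do not support either: section 18.2 lists three presentations, and a rebound past baseline or across a cut-off shows.

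Second, there are other routes. Worsening reported as an adverse event enters the SAP 17.1 tables by antibody status, which the change form restricts to treatment-emergent events. Protocol 8.3.8 asks for a neutralizing-activity sample at suspected loss of response. Protocol 10.5 plots titers, neutralizing results and exposure for each patient. With 10 patients (Protocol 4.2) or 11 (SAP 4.1), patient-level reading is realistic. So it would go too far to infer that the trial cannot show a link; what is missing is a prespecified analysis that shows it.

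These routes are incomplete. The 10.5 patient plots are not described as including HbA1c or triglycerides. Protocol 8.3.6 frames laboratory deterioration against baseline, and its sentence on how to report it is unfinished. Appendix A classes deterioration from lack of effect as not reasonably attributable to drug, which would keep such events out of the table of events possibly caused by metreleptin. The extra visualizations allowed in SAP 9 are discretionary.

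Third, the SAP 9 shells and part of the change form are not available. A listing or derivation there cannot be excluded, so the point is limited to the text that can be read.

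**Conclusion.** The point holds in this form: loss of response is a named safety outcome that the available SAP text does not derive, and the split by antibody status promised in Protocol 10.5 is absent from SAP 18.2 while SAP 4.3 declares no change. This is more than missing detail, because the SAP overrides the protocol.

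The size is illustrative. Under assumed courses, a worsening of 2.0 to 2.8 HbA1c points, or of 140% in triglycerides, from the best on-treatment value can leave change from baseline favourable and the category unchanged. How many patients are affected cannot be known from the documents. The conclusion assumes that the unseen shells and change-form pages add nothing on this point.

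**What to change.** 1. Restore to SAP 18.2 the Protocol 10.5 summaries of HbA1c and triglyceride change by peak antibody titer and by neutralizing category or percent inhibition. If they are to be dropped, say so in SAP 4.3.
2. Add a per-patient figure or listing in the safety analysis set: HbA1c and triglycerides over time, change from baseline, and change from the lowest earlier on-treatment value, beside same-visit binding titer, cell-based category and receptor-blocking result. Show metreleptin interruptions and dose changes, and changes in antidiabetic or lipid-lowering drugs, since any of these may explain a rise. Keep it continuous and descriptive, with no any-rise flag. State that a rise from a minimum is biased upward by noise, and that a rise first seen at Month 36 cannot be confirmed. The latter matters because Protocol 2.2 reports first Category D or E activity as late as 156 weeks.
3. Reconcile Protocol 8.3.8 with the AESI lists in Protocol 8.2 and SAP 17.1.
4. The change form already records changes made after database lock, so label these additions as post-lock.

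The cost is a little programming on data already collected and one noisy descriptive measure in the report.

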2.3 Benefit/Risk and Ethical Assessment

Native leptin is a hormone predominantly secreted by adipose tissue that informs the central nervous system of the status of energy stores in the body. In patients with generalized lipodystrophy, leptin deficiency, resulting from the loss of adipose tissue, contributes to excess caloric intake, which exacerbates the metabolic abnormalities leading to comorbid conditions including severe insulin resistance, diabetes, and hypertriglyceridemia. As reported in the USPI, MYALEPT is indicated as an adjunct to diet as replacement therapy to treat the complications of leptin deficiency in patients with congenital or acquired generalized lipodystrophy. Treatment with MYALEPT resulted in robust mean/median reductions in HbA1c, fasting glucose, and triglycerides at 1 year. The magnitude of these reductions was greater in patients with higher HbA1c, fasting glucose, and triglycerides prior to treatment (MYALEPT Prescribing Information).

T-cell lymphoma has been reported in patients with acquired generalized lipodystrophy, both treated and not treated with MYALEPT. The benefits and risks of treatment with MYALEPT in patients with significant hematologic abnormalities and/or acquired generalized lipodystrophy should be considered.

Anti-metreleptin antibodies with *in vitro* neutralizing activity have been identified in patients treated with MYALEPT. The consequences of these neutralizing antibodies are not well characterized but could include inhibition of endogenous leptin action and/or loss of MYALEPT efficacy. Severe infection and/or worsening metabolic control have been reported.

Confidential Page 18 of 60

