4.3 Inclusion Criteria

For inclusion in the study, patients should fulfill the following criteria at the screening visit:

- 1. Provision of informed consent prior to any study specific procedures. If <18 years of age, has a parent or guardian able to read, understand, and sign the Informed Consent Form (ICF) and a Child Assent form, communicate with the Investigator, and understand and comply with protocol requirements. Adolescent patients must also read and understand the Child Assent Form. If the child is too young or unable to read, then the Child Assent form must be explained to the child.
- 2. Female and/or male patients ≥ 1 years of age.
- 3. Physician-confirmed diagnosis of congenital or acquired generalized lipodystrophy and will begin treatment with MYALEPT for the first time.
- 4. Negative pregnancy test (urine or serum) for female patients of childbearing potential.
- 5. Female patients of childbearing potential must be 1 year postmenopausal, surgically sterile, or be willing to use an acceptable method of contraception (an acceptable method of contraception is defined as a barrier method in conjunction with a spermicide) for the duration of the study (from the time they sign consent). In addition, oral contraceptives, approved contraceptive implant, long-term injectable contraception, intrauterine device, or tubal ligation are allowed. Oral contraception alone is not acceptable; additional barrier methods in conjunction with spermicide must be used.
- 6. Male patients must be surgically sterile or be willing to use an acceptable method of contraception (defined as barrier methods in conjunction with spermicides) for the duration of the study (from the time they sign consent).
- 7. Patients who are blood donors should not donate blood during the study and for 3 months following their last dose of metreleptin.

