#### 8. STATISTICAL CONSIDERATIONS

### 8.1 Statistical Summaries, Tests and Confidence Intervals

There will be no hypothesis testing. All data will be summarized by descriptive statistics and/or listings. Number of patients with missing data will be reported where applicable. Continuous variables will be summarized by mean, standard deviation, median, minimum, and maximum. Categorical variables will be summarized by frequency counts and percentages of each category. Missing values will be excluded from percentage calculations. Where appropriate, two-sided, 90% and 80% Clopper-Pearson exact confidence intervals (CIs) will be included as well.

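### SAP 18.2: the third fasting glucose category appears to have its sign reversed, so values below 100 mg/dL are counted twice and values above 100 mg/dL are not counted at all

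*SAP*

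**What the plan says.** SAP section 18.2 lists four exploratory variables: HbA1c, fasting plasma glucose, triglycerides and leptin/metreleptin concentration. All four are described at each visit and "as absolute change from baseline and percent change from baseline at each visit". A further instruction covers three of them: "HbA1c, fasting plasma glucose, and triglycerides will also be summarized by clinically relevant categories at each visit". For glucose the categories are "fasting plasma glucose (<70 mg/dL, >=70 mg/dL and <=100 mg/dL, <100 mg/dL". For triglycerides they are "triglycerides (<500 mg/dl, >=500 mg/dl", and HbA1c is split at 8% in the same way.

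SAP section 8.1 fixes how such a table is filled: "Categorical variables will be summarized by frequency counts and percentages of each category". It also says that missing values are left out of percentages.

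The protocol gives no glucose cut-points. It collects fasting glucose (section 7.1) but names only HbA1c and fasting triglycerides as efficacy outcomes (sections 3.4 and 10.4). The SAP modification history shows that glucose became an exploratory variable in version 2.0. SAP 18.2 is therefore the only available source of this rule. The version 2.1 entry and the available parts of the later change form do not mention glucose.

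**The concern.** A categorical summary needs each observed value to fall in one category and only one. The first two glucose categories already cover everything up to and including 100 mg/dL. The third should take what is left, but it covers values below 100 again. The upper range has no category.

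The upper range matters for reading the table. Protocol section 2.3 describes "comorbid conditions including severe insulin resistance, diabetes, and hypertriglyceridemia" in generalized lipodystrophy and cites reductions in fasting glucose under treatment. A by-visit table with no category above 100 mg/dL cannot show patients leaving that range. The rule also leaves the programmer to guess, so two programmers could produce different tables from the same data.

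**Working it through.** **Inputs.** The three conditions come from SAP 18.2: (1) below 70; (2) at least 70 and at most 100; (3) below 100 mg/dL. Counts and percentages per category come from SAP 8.1. The plan states no figure to reproduce, and power and alpha do not arise: "There will be no hypothesis testing".

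**Step 1: which conditions each value meets.**

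| Fasting glucose (mg/dL) | Conditions met | Number |
|---|---|---|
| below 70 | 1 and 3 | 2 |
| 70 to below 100 | 2 and 3 | 2 |
| exactly 100 | 2 | 1 |
| above 100 | none | 0 |

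**Step 2: count over a wide range.** Take every whole number from 20 to 600, which is 581 values.

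- Counted twice: 20 to 69 (50 values) plus 70 to 99 (30 values) = 80.
- Counted once: the value 100 = 1.
- Not counted: 101 to 600 = 500.
- Check: 80 + 1 + 500 = 581.

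This describes the rule, not patients; the values are not weighted by how often they occur.

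**Step 3: effect on the percentages.** Let q be the share of non-missing values above 100 mg/dL, and assume that none is exactly 100. Each of the remaining 1 − q is counted twice, so the category percentages add to 2 × (1 − q) × 100 = 200(1 − q)%. The documents do not give q, so the full range is shown.

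| q (assumed) | Unclassified | Counted twice | Sum of percentages |
|---|---|---|---|
| 0 | 0% | 100% | 200% |
| 0.25 | 25% | 75% | 150% |
| 0.50 | 50% | 50% | 100% |
| 0.75 | 75% | 25% | 50% |
| 0.90 | 90% | 10% | 20% |
| 1 | 100% | 0% | 0% |

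At q = 0.5 the percentages add to 100% by coincidence, although every value is still either counted twice or left out. A correct total would therefore not prove the table right.

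**Step 4: other ways to program it.** If the conditions are tested in order and each value stops at the first match, nothing is double-counted. The third category is then always empty, and values above 100 remain unclassified. If the last step is a catch-all, values above 100 appear in a row labelled as below 100. The written rule does not say which of these applies.

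**Step 5: the repair.** With the third condition as above 100 mg/dL, the same 581 values split into 50 (20 to 69), 31 (70 to 100) and 500 (101 to 600). These add to 581, and each value is counted once.

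**The case against.** The strongest reply is that this is a typing slip with an obvious reading. The HbA1c and triglyceride categories beside it divide their scales correctly, and once below 70 and 70 to 100 are set, the only sensible third band is above 100. SAP section 9 leaves the format and content of tables to a shell document, which may be right. SAP section 5 plans a dry run on real data before database lock, where a table with no upper band would probably be noticed. Part of the change form is not available. In the text copy of the SAP, the footer date just below this line is garbled, so a corrupted character is possible; a look at the signed document settles that.

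Much of this stands. It supports calling the fault a reversed sign and keeping its weight low. It does not make the rule correct: SAP 18.2 is the authorized text, and nothing available amends it. The other signs on the same line make sense, which weakens the corrupted-character explanation.

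A reader might also infer more than the documents support:

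- **That the table fails for most of a diabetic population.** Diabetes is described as a comorbidity. The entry criterion is "Physician-confirmed diagnosis of congenital or acquired generalized lipodystrophy", with no diabetes or glucose requirement, and no baseline glucose distribution is given. The share above 100 mg/dL cannot be computed.
- **That unclassified values drop out of the denominator.** SAP 8.1 excludes missing values. An observed glucose above 100 mg/dL is not missing, and nothing in that section treats it as such.
- **That the study's assessment of glycaemia is lost.** Glucose is still summarized by visit and as change from baseline, and HbA1c has its own valid categories.

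**Conclusion.** The point holds for the SAP text. The glucose categories overlap for every value below 100 mg/dL and omit every value above it; only exactly 100 mg/dL is classified once. This follows from the three conditions alone and does not depend on the patients' glucose values. How far the printed percentages would be wrong does depend on them, and that size is unknown.

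The reach is one exploratory, descriptive table in a study of 10 (protocol 4.2) or 11 (SAP 4.1) patients. The continuous glucose summaries, the HbA1c and triglyceride summaries, the primary immunogenicity analysis and the safety analyses do not use these cut-points.

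The conclusion assumes that the sign in the SAP is as printed, and that neither the table shells nor the unavailable part of the change form already corrects it. It is worth correcting because the rule is wrong as written and the repair is simple, not because a main conclusion depends on it.

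**What to change.** In SAP 18.2, change the third fasting plasma glucose category to above 100 mg/dL, so that the three are below 70, 70 to 100 inclusive, and above 100 mg/dL. Confirm that the table shell and the program use the same three conditions, and check in the output that the category counts add to the number of non-missing values at each visit.

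Record the correction in the SAP change record and in the study report; SAP section 2 already requires departures from the final plan to be reported. The change form carries entries dated after database lock, so there is a route for a late correction.

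The cost is one character in the SAP, a check of the shell and program, and a rerun of one table if the program followed the printed rule. No new data are needed.
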